5.1 Inclusion criteria

Patients are eligible to be included in the study only if all of the following inclusion criteria and none of the exclusion criteria apply:

1. Men and Women aged 18 yrs or more.
2. Eastern Cooperative Oncology Group (ECOG) performance status of 0,1, or 2
3. Able to receive all outpatient treatments, all laboratory monitoring, and all radiologic evaluations.
4. The following laboratory parameters:
 - a. Absolute neutrophil count (ANC) ≥ 750 cells/ μL or ≥ 500 cells/ μL in patients with documented bone marrow involvement, and independent of growth factor support 07 days before the assessment
 - b. Platelet count $\geq 50,000$ cells/ μL or $\geq 30,000$ cells/ μL in patients with documented bone marrow involvement, and without transfusion support 07 days before the assessment
 - c. Aspartate transaminase (AST) and Alanine transaminase (ALT) ≤ 2.0 x ULN

- d. Total bilirubin $\leq 1.5 \times$ ULN
 - e. Estimated creatinine clearance of ≥ 30 mL/min
5. Refractory disease defined as achieving less than partial response with the most recent treatment before study entry
 6. Provision of signed, written and dated informed consent prior to any study-specific procedures
 7. The patients of either CLL or MCL:
 - a. **CLL patients:**
 - i. Treatment naïve or ≥ 1 prior systemic therapy for CLL
 - ii. Diagnosis of CD20+ CLL that meets published diagnostic criteria (Hallek et al. 2018)
 - iii. An active disease that meets ≥ 1 of the following iwCLL 2018 criteria for requiring treatment
 - 1) Evidence of progressive marrow failure as manifested by the development of, or worsening of, anaemia and/or thrombocytopenia. Cut-off levels of Hb < 10 g/dL or platelet counts $< 100 \times 10^9/L$ are generally regarded as an indication for treatment. However, in some patients, platelet counts $< 100 \times 10^9/L$ may remain stable over a long period; this situation does not automatically require therapeutic intervention.
 - 2) Massive (i.e., ≥ 6 cm below the left costal margin) or progressive or symptomatic splenomegaly.
 - 3) Massive nodes (i.e., ≥ 10 cm in longest diameter) or progressive or symptomatic lymphadenopathy.

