8.1 Efficacy and Safety assessments

8.1.1 Efficacy Assessment

Objective Response

All patients who receive Acalabrutinib capsule 100 mg BID will be evaluated for efficacy once every 03 months during the treatment phase. The following assessments must be performed every three treatment cycles: tumour assessment, ECOG performance status, and partial remission (PR), partial response with lymphocytosis (PR-L) and complete remission (CR).

A characteristic feature of BTK inhibitor is that it may transiently increase the peripheral lymphocyte count while the lymph nodes are shrinking and patients are improving. Some patients were taken off study very early in ibrutinib trials because their lymphocyte count began to go up and it was assumed that they were progressing. The transient lymphocytosis is now understood to be an effect of redistributing parts of the disease into the blood. It is not considered as a sign of disease progression. There is now a response criterion known as PRL, which refers to patients who have a greater than 50% shrinkage of nodal disease and who fulfil all criteria of partial response (PR) except for a persistent lymphocytosis. (Woyach et al., 2014) In the present study the objective response will evaluate PR, PR-L, and CR.

The efficacy endpoint will be objective response, defined as the proportion of patients achieving either a PR or CR per the iwCLL 2018 criteria for CLL/SLL (Hallek et al., 2018) and Lugano classification for NHL for MCL (Cheson et al., 2014) as presented in Table 4 and Table 5, respectively. Efficacy will be based on objective response [Complete Remission (CR) + Partial Remission (PR)] via Computed Tomography (CT) scans or Magnetic Resonance Imaging (MRI).

Table 4: Response (CR and PR) definition after treatment of CLL/SLL patients (Hallek et al., 2018)

Parameter	Complete Remission (CR)	Partial Remission (PR)
Lymph nodes	None ≥ 1.5 cm	Decrease $\geq 50\%$ from baseline*
Liver and/or spleen size†	Spleen size < 13 cm; liver size normal	Decrease $\geq 50\%$ from baseline
Constitutional symptoms	None	any
Circulating lymphocyte count	Normal	Decrease $\geq 50\%$ from baseline
Platelet count	$\geq 100 \times 10^9/L$	$\geq 100 \times 10^9/L$ or increase $\geq 50\%$ over baseline
Haemoglobin	≥ 11.0 g/dL (untransfused and without erythropoietin)	≥ 11.0 g/dL or increase $\geq 50\%$ over baseline

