Creatinine (creatinine clearance)
Urea or Blood Urea Nitrogen, depending on local practice
Gamma-glutamyl transferase
Magnesium
Haptoglobin
b2-microglobulin

Note: CMV serology, HIV (anti-HIV1 Ab, anti-HIV2 Ab), Hepatitis serology testing will be conducted at the screening that includes hepatitis B surface antigen (HBsAg), hepatitis B surface antibody (HBsAb), anti-HBc, and HCV antibody.

The local GLP certified laboratory will perform haematology and clinical chemistry tests. Additional analyses may be performed if clinically indicated.

Any clinically significant abnormal laboratory values should be repeated as clinically indicated and recorded in the eCRF.

All patients who have any Common Toxicity Criteria (CTC) Grade 3 or 4 laboratory values at the time of completion or discontinuation from study must have further tests performed until the laboratory values have returned to CTC Grade 1 or 2, unless these values are not likely to improve because of the underlying disease.

Urine Pregnancy Test

Urine pregnancy tests will be required only for women of childbearing potential. Urine pregnancy tests will be performed at Screening; on Cycle 1 Day 1; on Day 28 of Cycles 1-6; and at the early termination or End of study visit.

Physical examinations

For timing of individual measurements refer to the schedule outlined in (Table 1).

A complete physical examination will be performed and will include an assessment of the following (as clinically indicated): general appearance, respiratory, cardiovascular, abdomen, skin, head, neck (including ears, eyes, nose, and throat), lymph nodes, thyroid, musculoskeletal (including spine and extremities), and genital/rectal and neurological systems.

Symptom-directed physical exams, including tumour assessments by palpation, will be done during the treatment period and at the EOT visit.

Lymph nodes: The bi-dimensional diameters of the largest palpable lymph node/s in each of the following sites should be recorded: cervical, axillary, and inguinal. The dimensions of the liver and spleen below their respective costal margins, as assessed by palpation, should also be recorded.

Performance status will be assessed using ECOG performance status.

Vital signs

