8.2.7 Adverse events based on examinations and tests

The results from the Clinical Study Protocol-mandated laboratory tests and vital signs will be summarised in the CSR. Deterioration as compared to baseline in protocol-mandated laboratory values, vital signs should, therefore, only be reported as AEs if they fulfil any of the SAE criteria or are the reason for discontinuation of treatment with the investigational product.

If deterioration in a laboratory value/vital sign is associated with clinical signs and symptoms, the sign or symptom will be reported as an AE, and the associated laboratory result/vital sign will be considered as additional information. Wherever possible, the reporting Investigator will use the clinical, rather than the laboratory term (e.g., anaemia versus low haemoglobin value). In the absence of clinical signs or symptoms, clinically relevant deteriorations in non-mandated parameters should be reported as AE(s).

Deterioration of a laboratory value, which is unequivocally due to disease progression, should not be reported as an AE/SAE.

Any new or aggravated clinically relevant abnormal medical finding at a physical examination as compared with the baseline assessment will be reported as an AE unless unequivocally related to the disease under study.

Disease progression can be considered as a worsening of a patient's condition attributable to the disease for which the investigational product is being studied. It may be an increase in the severity of the disease under study and/or increases in the symptoms of the disease. The development of new, or progression of existing metastasis to primary cancer under study should

be considered as disease progression and not an AE. Events, which are unequivocally due to disease progression, should not be reported as an AE during the study.

New cancers

The development of new cancer should be regarded as an SAE. New primary cancers are those that are not the primary reason for the administration of the study drug and have been identified after the patient's inclusion in this study.

Deaths

All deaths that occur during the study, or within the protocol-defined follow-up period after the administration of the last dose of study drug, must be reported as follows:

- Death clearly the result of disease progression should be reported to the study monitor at the next monitoring visit and should be documented in the eCRF but should not be reported as an SAE.

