#### 6.3.1 Primary Endpoint Analysis

Primary Endpoint evaluations will include adverse event monitoring, physical examinations, ECG monitoring, clinical laboratory investigations (haematology and biochemistry), vital sign measurements, ECOG performance status and death as observed by the Investigator.

Adverse Events (AEs), Serious Adverse Events (SAEs), and AEs of Special Interest (AESI) will be summarized using frequencies and percentages.

Physical examination will be collected as per visit scheduled. Physical examination results (normal /abnormal) from scheduled visits will be summarized for each body system. A listing will be provided for the Normal/abnormal physical examination parameters.

A 12-lead electrocardiogram (ECG) will be performed as per visit scheduled. ECG results (normal, abnormal clinically insignificant, abnormal clinically significant) will be summarized as counts and percentage.

Laboratory investigations (haematology and biochemistry) data will be collected as per visit scheduled. Laboratory values will be presented using the International System of Units (SI units). Observed values will be summarized descriptively (n, mean, median, standard deviation, minimum, and maximum values). A listing will be provided which contains data for each laboratory parameter.

Document Title:	Document ID:	BP04-01
Statistical Analysis Plan	Version Number:	3.1
	Effective Date:	25-Nov-2021

Vital signs will be performed as per visit scheduled. Vital signs parameters include Systolic Blood Pressure, Diastolic Blood Pressure, Heart Rate, Respiratory rate and Temperature. Descriptive summaries (n, mean, median, standard deviation, minimum and maximum values) of observed values in each vital sign parameter at each assessment visit will be presented. A listing will be provided for all vital signs parameters assessments.

ECOG will be performed as per visit scheduled. ECOG performance status will be summarized as counts and percentage.

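### Laboratory and vital-sign tables show only observed values by visit, so patients whose values worsened without an adverse event being recorded can be traced in listings but are counted in no table

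*SAP*

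**What the plan says.** SAP section 6.3.1 counts laboratory tests and vital signs among the primary endpoint evaluations. For laboratory values the method is "Observed values will be summarized descriptively (n, mean, median, standard deviation, minimum, and maximum values"; for vital signs, summaries "of observed values in each vital sign parameter at each assessment visit will be presented". Tables 14.3.4.1 (haematology), 14.3.4.2 (biochemistry) and 14.3.5 (vital signs) follow this for Visits 1 to 8: n, missing, mean (SD), median, minimum and maximum. Their only counted row is whether the sample or measurement was taken.

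Listings 16.2.15.1, 16.2.15.2 and 16.2.16 carry a Finding column for each patient and parameter. No table uses it.

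Protocol section 8.2.7 sets the AE rule: "Deterioration as compared to baseline in protocol-mandated laboratory values, vital signs should, therefore, only be reported as AEs" if they meet a seriousness criterion or lead to discontinuation. The reason it gives is that "The results from the Clinical Study Protocol-mandated laboratory tests and vital signs will be summarised in the CSR". Where symptoms are present, the symptom is the AE.

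Protocol section 8.1.2 treats individual laboratory values as clinically meaningful. "All patients who have any Common Toxicity Criteria (CTC) Grade 3 or 4 laboratory values at the time of completion or discontinuation from study" must be retested, with an exception for the underlying disease. It adds: "Any clinically significant abnormal laboratory values should be repeated as clinically indicated and recorded in the eCRF".

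**The concern.** The trial has one arm, so a patient's own pre-dose value is the only comparator for a laboratory value or blood pressure. An observed value alone is hard to read in this population. One qualifying criterion in protocol section 5.1 is "Evidence of progressive marrow failure as manifested by the development of, or worsening of, anaemia and/or thrombocytopenia", so patients may start with low counts. Haemoglobin is also expected to rise in responders: protocol Table 4 requires at least 11.0 g/dL, "untransfused and without erythropoietin", for complete remission. A haemoglobin of 9 g/dL on treatment could therefore be a fall, no change or a recovery.

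Anaemia and hypertension are named AEs of special interest in the primary endpoint. Asymptomatic falls in haemoglobin and rises in blood pressure bear on them, and these are the deteriorations that section 8.2.7 allows sites to leave out of the AE record. The tables that section 8.2.7 relies on instead contain no comparison with baseline. What is at stake is the completeness of the safety description.

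**Working it through.** **The texts side by side.**

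1. Protocol 8.2.7 removes from AE reporting any deterioration in a mandated laboratory value or vital sign that is asymptomatic, non-serious and does not cause discontinuation, and points to the study report's summary.
2. In SAP 6.3.1 and the three mock tables, that summary has no comparison within the patient. Minimum and maximum show one extreme patient per visit; n and missing show who is absent. Neither gives the number who worsened.
3. The SAP defines no baseline. Visit 1 is screening and Visit 2 is Cycle 1 Day 1. Haematology and biochemistry need not be repeated at Visit 2 if screening was within 5 days, so neither column is consistently the last pre-dose value.
4. The tables stop at scheduled visits. Repeats recorded under protocol 8.1.2 may hold the worst value and fall outside them.
5. The SAP uses suitable tools elsewhere. Table 14.3.2 counts normal and two grades of abnormal for physical examination, and Listing 16.2.9.1 carries percentage change from Visit 1 for imaging.

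**The plan's own figures.** No stated figure bears directly on this point. The only precision calculation is protocol Table 8, with exact (Clopper-Pearson) intervals. For 10 of 100, the lower limit is the 0.025 quantile of Beta(10, 91) and the upper the 0.975 quantile of Beta(11, 90), giving 4.90% to 17.62% as printed. All 43 cells reproduce to within 0.011 percentage points.

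**Illustrations.** Every haemoglobin input below is assumed.

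*A. Identical visit summaries.* Of 100 patients, 10 fall from 12 to 9 g/dL, 10 rise from 9 to 12 and 80 stay at 10.
- Mean at both visits: (10×12 + 10×9 + 80×10)/100 = 10.1.
- SD at both visits: √[(10×1.9² + 10×1.1² + 80×0.1²)/99] = √(49.0/99) = 0.70.
- Median 10, minimum 9 and maximum 12 at both visits.
- A shift row would show 10/100 = 10% (4.90% to 17.62%) falling by at least 2 g/dL. The planned table shows no difference.

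*B. Same mean and SD at two visits, correlation r.* With SD 2 g/dL and bivariate normal values, the SD of change is 2√[2(1−r)] and the share falling by at least 2 g/dL is Φ(−2/SD of change). For r = 0.3, 0.6 and 0.9 this is 19.9%, 13.2% and 1.3%. By-visit summaries cannot separate these cases.

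*C. Falls offset by rises.* N = 90, mean 10.5, SD 2. A fraction q falls by 2 g/dL and the rest rise by 2q/(1−q), independently of starting value.
- q = 0.10 (9 patients): rise 0.222; visit SD √(4 + 0.10×4 + 0.90×0.222²) = 2.11.
- q = 0.20 (18 patients): rise 0.500; visit SD √(4 + 0.20×4 + 0.80×0.5²) = 2.24.
- The visit mean stays 10.5 and mean change is 0. Fallers newly below 10 g/dL: Φ(0.75) − Φ(−0.25) = 0.372, times 9 or 18, is about 3 to 7 patients.

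*D. Low at a single visit.* The same 9 or 18 patients are each 2 g/dL low at one of Visits 3 to 8. Mean change per visit is −2q/6 = −0.03 or −0.07 g/dL, with 1.5 or 3 patients low at a time. A baseline-to-worst row counts all 9 or 18.

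*E. Change in who is measured.* If a fraction p is absent and their baseline is d lower than that of the whole group, the visit mean moves by pd/(1−p) with no true change. For p = 0.05, d = 1 g/dL: 0.05. For p = 0.15, d = 2 g/dL: 0.35 g/dL, or 0.18 SD.

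C and D show that the mean of by-visit change can also miss the signal, so the worst-value shift is the more useful addition. E is what change in patients with both values corrects.

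**The case against.** **The plan breaches nothing.** Protocol 8.2.7 promises a summary and section 9.4 promises descriptive statistics; the SAP supplies both. This stands. A reader might infer that the SAP departs from the protocol, but neither document requires change or shift rows.

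**Other routes lead into the AE data.** Protocol section 8.2 covers events derived from safety assessments, and Appendix B 1 lets an abnormal laboratory finding be an AE. Appendix C treats Grade 4 thrombocytopenia, and Grade 4 neutropenia beyond 7 days, as adverse reactions requiring interruption. Seriousness includes important medical events, which leaves room for judgement, and sites may record the named events of special interest anyway. This stands as a limit. A reader might infer that all asymptomatic deterioration is missing from the safety analysis. The documents support less: the clear residue is milder, non-serious change, its extent depends on which text sites follow, and the individual values remain in the listings.

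**ECG does not belong.** A reader might extend the argument to ECG intervals because Table 14.3.3 also shows observed values only. The documents do not support that. Protocol 8.1.2 makes clinically significant ECG abnormalities AEs and names QTc above 480 ms among them. SAP 6.3.1 already promises counts of normal and abnormal ECGs; Table 14.3.3 merely lacks the row.

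**The size is assumed.** This stands. Nothing in the documents says how often such deterioration will occur.

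**Conclusion.** The point holds as a minor, cheap improvement for laboratory values and vital signs. The planned tables cannot show how many patients worsened from their own baseline. To the extent that sites apply section 8.2.7, some of those patients will not appear in the AE tables either.

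The magnitude is unknown. The illustrations show what the planned layout can conceal under assumed haemoglobin values; they do not estimate what it will conceal. The effect on visit means is probably small. A reader might infer that the primary result is biased, but AE incidence as the protocol defines it is unaffected and no hypothesis is tested on these means. What is missing is a count of patients that the collected data could largely provide.

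**What to change.** In SAP section 6.3.1, define baseline as the last non-missing value before the first dose. In Tables 14.3.4.1, 14.3.4.2 and 14.3.5 add:

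- **Main addition:** a baseline-to-worst on-treatment summary, including early end-of-treatment and unscheduled values.
- **Second:** change from baseline at each post-baseline visit in patients with both values.

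For the laboratory shift, use CTCAE 5.0 (Appendix B 6) and note that Appendix C uses 4.03 for dose modification. Take the worst low value for haemoglobin, platelets and absolute neutrophil count, and the worst high for ALT, AST and bilirubin. Table 14.3.4.2 gives creatinine in mL/min/1.73m², a clearance unit, so take the worst low there; use worst high only if serum creatinine is reported.

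Grades set against limits of normal need local reference ranges, and the laboratory listings have no column for them. Where the eCRF lacks ranges, count patients by baseline versus worst Finding flag, using the normal and two abnormal categories of Table 14.3.2 (assuming the laboratory flag is coded that way). For blood pressure, use the same flag shift or categories named in the SAP.

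Separately, add the promised normal/abnormal row to Table 14.3.3.

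The cost is SAP wording, extra programming and use of local-laboratory ranges where recorded. No extra visits are needed, and the data are largely already collected.

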### 6.3.2 Secondary Endpoint Analysis

Secondary Endpoint evaluations will be assessed based on iwCLL 2018 criteria for CLL/SLL and for MCL. Efficacy will be based on objective response [Complete Remission (CR) + Partial Remission (PR) and Partial response with lymphocytosis (PRL)] via Computed Tomography (CT) scans or Magnetic Resonance Imaging (MRI). The sum of complete response and partial responses and Partial response with lymphocytosis (PRL)] will be summarized using frequencies, percentage and 95% CI will be calculated using Clopper Pearson confidence interval method. Health related quality of life (EORTC QLQC30 Questionnaire) summarized using frequencies and percentage.

## 8. Mock Tables

Table 14.1.1. Patient Disposition in the Study

	CLL/SLL (N=xx)	MCL (N=xx)	Total (N=xx)
	n (%)	n (%)	n (%)
Patients Screened	xx (xx.xx)	xx (xx.xx)	xx (xx.xx)
Screen Failures	xx (xx.xx)	xx (xx.xx)	xx (xx.xx)
Patients Completed the study	xx (xx.xx)	xx (xx.xx)	xx (xx.xx)
Patients Discontinued the study	xx (xx.xx)	xx (xx.xx)	xx (xx.xx)
Reason for Discontinuation			
Patient Decision	xx (xx.xx)	xx (xx.xx)	xx (xx.xx)
Adverse Event	xx (xx.xx)	xx (xx.xx)	xx (xx.xx)
Severe non-compliance to study protocol	xx (xx.xx)	xx (xx.xx)	xx (xx.xx)
Initiation of alternative anticancer therapy including another investigational agent	xx (xx.xx)	xx (xx.xx)	xx (xx.xx)
Disease progression	xx (xx.xx)	xx (xx.xx)	xx (xx.xx)
Pregnancy or intent to become pregnant	xx (xx.xx)	xx (xx.xx)	xx (xx.xx)
Other	xx (xx.xx)	xx (xx.xx)	xx (xx.xx)
Other 1	xx (xx.xx)	xx (xx.xx)	xx (xx.xx)
Other 2	xx (xx.xx)	xx (xx.xx)	xx (xx.xx)

- The Capital "N" in the column header represents the total number of all Enrolled Patients.
- The small "n" in summary statistics represents the total number of Patients.
- Percentages in the "Patients Screened", "Screen Failures", "Patient completed the study" and "Patients Discontinued the study" rows are based on the number of Patient in each group.
- Percentages in the "Reasons for Discontinuation" rows are based on the number of Patients Discontinued study in each group.
- Note: Screened Patients are those who signed the informed consent
- Source :Listing 16.2.1.1, listing 16.2.1.2

Document Title:	Document ID:	BP04-01
Statistical Analysis Plan	Version Number:	3.1
	Effective Date:	25-Nov-2021

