1.2 Synopsis

Protocol Title: A prospective, multi-centre, phase IV clinical trial to assess the safety and efficacy of Acalabrutinib capsules in Indian adult patients with chronic lymphocytic leukaemia and relapsed and refractory mantle cell lymphoma

Version: 1.0 Date: 01 Sep 2020

Study sites and number of patients planned

No. of total screened patients: Approximately 150

No. of total enrolled patients: Approximately 100

No. of study sites: 10

Total planned study period	
Estimated date of the first patient in	Q4 2020
Estimated date of the last patient in	Q2 2021
Estimated date of last patient last visit	Q4 2021
Estimated date of database lock	Q2 2022
Clinical study report	Q3 2022

Rationale

Chronic lymphocytic leukaemia (CLL) is a malignancy of B cells that predominantly affects an elderly population. It is the most prevalent form of adult leukaemia, with an age-adjusted incidence of 3.3–6.4 per 100,000 person-years and a median age at diagnosis of 70 years (Noone AM, April 2018). The diagnosis of CLL is established using peripheral blood and immunophenotyping and requires the presence of a minimum of $5 \times 10^9/L$ monoclonal B cells that co-express the surface antigens CD5, CD19, CD20, and CD23. In routine practice, patients with asymptomatic early-stage disease should be monitored without therapy unless they have evidence of disease progression or disease-related symptoms. Treatment of CLL is initiated once there is evidence of progressive or symptomatic/active disease as defined by iwCLL guidelines (Hallek et al., 2018; Hallek et al., 2008). Despite the relatively long life expectancy for early-stage disease, CLL remains an incurable disease.

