5.4 Screen failures

Screen failures are defined as patients who sign the informed consent form to participate in the clinical study but are not subsequently entered in the study. A minimal set of screen failure information is required to ensure transparent reporting of screen failure patients to meet the Consolidated Standards of Reporting Trials (CONSORT) publishing requirements and to respond to queries from regulatory authorities. Minimal information includes demography, screen failure details, and eligibility criteria. The reason/s for screen failure for these patients should be recorded in the electronic Case Report Form (eCRF).

Individuals who do not meet the criteria for participation in this study (screen failure) may not be rescreened.

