### 2.2 Study Description

#### 2.2.1 Study Design

The study is a phase IV, open-label, single-arm, multi-centre, prospective study to be conducted in India. The study will evaluate the safety and efficacy of Acalabrutinib in Indian adult Patients with CLL/SLL and Patients with MCL who have received at least one prior therapy. The Investigator will be trained on the locally approved Prescribing Information (PI) before the enrolment of the first Patient at their site to ensure compliance and proper dosing of the study drug. Patients will be monitored throughout the study period for AEs /SAEs/AESI of Acalabrutinib.

Patients with CLL/SLL and MCL who are eligible to receive Acalabrutinib treatment as per locally approved PI and ratified by an independent clinical judgment of treating physician will be evaluated for inclusion into the current phase IV trial. To enrol approximately 100 Patients (90 Patients of TN & R/R CLL and 10 R/R MCL Patients) into the study, it is expected that approximately 150 Patients will need to be screened.

The study will be initiated after approval by the Ethics Committee. Patients will undergo the following phases: Screening/Enrolment Phase, Treatment Phase, and Follow-up Phase.

Document Title:	Document ID:	BP04-01
Statistical Analysis Plan	Version Number:	3.1
	Effective Date:	25-Nov-2021

The decision of Patients to participate in this study must not, in any way, impact the standard of care they are receiving or any benefits to which they are otherwise entitled. Prior to data collection, all Patients must sign an Informed Consent Form (ICF), allowing for data collection and source data verification to be performed in accordance with local requirements and Sponsor policy.

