##### 5.3 Disposition of Patients

Patient disposition table will be based on all enrolled Patients who consented to participate in the study. The following summaries will be included in the disposition table: total number of Patients screened in the study, number and percentage of Patients who failed screening, number and percentage of Patients who completed the study, and number and percentage of Patients who discontinued from the study with reason for discontinuation.

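### SAP Table 14.1.1 divides screened patients and screen failures by the enrolled N; at the planned totals this gives 150% screened and a 50% screen-failure rate instead of 33.33%

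*SAP*

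**What the plan says.** Two footnotes under SAP Table 14.1.1 set the denominators. The first says that the capital N in the "column header represents the total number of all Enrolled Patients". The second names the screened, screen-failure, completed and discontinued rows and says that percentages in these "rows are based on the number of Patient in each group". Only the reasons for discontinuation have a denominator of their own, the patients who discontinued. All of these rows are laid out as a count with a percentage.

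A note to the same table reads: "Screened Patients are those who signed the informed consent". Protocol Section 5.4 defines screen failures as "patients who sign the informed consent form to participate in the clinical study but are not subsequently entered in the study".

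SAP Section 5.3 says: "Patient disposition table will be based on all enrolled Patients who consented to participate in the study". It then asks for screened patients as a total, without a percentage, and for a number and percentage of screen failures, completers and discontinuations. It does not say what the screen-failure percentage is a percentage of.

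The planning numbers are in the Protocol synopsis (Section 1.2): "No. of total screened patients: Approximately 150" and "No. of total enrolled patients: Approximately 100". SAP Section 2.2.1 splits the enrolled total as "90 Patients of TN & R/R CLL and 10 R/R MCL Patients".

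**The concern.** A percentage makes sense here only if the patients counted belong to the group they are divided by. Screened patients are everyone who consented, a larger group than the enrolled. Screen failures are the consenting patients who were not enrolled, so none of them is in N. A programmer who follows the footnotes would print a screened percentage above 100 whenever anyone fails screening. The screen-failure figure would be a ratio of failures to enrolled patients, which a reader would take for a rate.

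At stake is the screen-failure rate in the first table of the report. Protocol Section 5.4 wants screen failures reported transparently, to meet CONSORT publication requirements and to answer regulators' questions. An inflated rate works against that purpose.

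**Working it through.** The plan prints no percentage to reproduce, because the shell contains only placeholders. The check applies the footnote rule to the planned totals.

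**Inputs**
- Screened: about 150 (Protocol synopsis).
- Enrolled: about 100 (Protocol synopsis). The cohort split agrees: 90 + 10 = 100.
- Screen failures: 150 − 100 = 50. By the Section 5.4 definition, everyone who consents and is not entered counts as a screen failure.

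**Formula:** row percentage = 100 × count / denominator.

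| Row (Total column) | N = enrolled (100), as footnoted | N = all consented (150) |
|---|---|---|
| Screened | 150/100 = 150.00% | 150/150 = 100% |
| Screen failures | 50/100 = 50.00% | 50/150 = 33.33% |
| Completed + discontinued, at most | 100/100 = 100% | 100/150 = 66.67% |

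The first column is what the footnotes say. It makes the two screening rows wrong and leaves the completion rows right. The second column is the result if N were every consenting patient: the screening rows come right and the completion rows are diluted. One denominator cannot serve both pairs of rows.

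**Sensitivity.** Both planning numbers are approximate, so I assumed 140 to 160 screened and 95 to 105 enrolled.
- Screened/enrolled runs from 140/105 = 133.3% to 160/95 = 168.4%, above 100% throughout.
- Screen failures/enrolled runs from 35/105 = 33.3% to 65/95 = 68.4%.
- Screen failures/screened runs from 35/140 = 25.0% to 65/160 = 40.6%.

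**Cohort columns.** Screening numbers by cohort are not given. The 150% and 50% would also appear in the CLL/SLL and MCL columns only if screening were proportional (135 screened for 90 enrolled and 15 for 10), which is an assumption.

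**The case against.** The best defence is that the slip is confined to two rows and is easy to see. The counts are printed beside the percentages, so a reader can work out 50/150, and a value above 100% would stand out when the tables are checked. SAP Section 5.3 already asks for screened patients as a total only, so the 150% comes from the shell and its footnote and not from the SAP text. This stands, and it keeps the point minor. It does not remove it: a 50% screen-failure rate looks plausible and would not draw the attention that 150% would.

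Two stronger readings are tempting.

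- *Completion and discontinuation rates are wrong too.* A reader might infer this from the Section 5.3 phrase about enrolled patients who consented, by taking N as all consented patients. With an assumed 90 completers and 10 discontinuers, completion would then read 90/150 = 60% instead of 90%, and discontinuation 10/150 = 6.67% instead of 10%. The documents do not support this. The table's own footnote defines N as enrolled patients, and with that N both rows are right. The 90/10 split is not in the documents.
- *The table cannot be tied to the Full Analysis Set (FAS).* A reader might infer this because no row shows enrolled or dosed patients. But the column header of Table 14.1.1 is the enrolled count, and that of Table 14.1.2 is the FAS count, so the two can be compared directly.

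**Conclusion.** The denominator rule is wrong as written for the screened and screen-failure rows of Table 14.1.1. At the planned totals it implies 150% screened and a 50% screen-failure rate where 33.33% is correct, an overstatement of 50.00 − 33.33 = 16.67 percentage points.

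This rests on three things: the group count in the second footnote is the header N, the only group count the table defines; the approximate planning totals are taken at face value; and the figures apply to the Total column.

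The consequence is limited to the presentation of screening. Completed and discontinued patients are correctly based on enrolled N, and the reasons for discontinuation keep their own denominator. The FAS, the adverse event percentages and the response rates do not change.

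**What to change.** In SAP Table 14.1.1 and Section 5.3:

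1. Change the footnote so that the screen-failure percentage is based on patients screened, meaning those who signed consent.
2. Show screened patients as a count with no percentage, which brings the shell into line with Section 5.3.
3. Keep enrolled N as the denominator for completed and discontinued patients, and name it in the footnote.
4. Reword the opening of Section 5.3 so that the screening rows use consented patients and the completion rows use enrolled patients.

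Rows for enrolled patients and for patients who received at least one dose would show the path from screening to the FAS in one place, but they are optional.

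The cost is wording in one shell, its footnotes and one SAP paragraph. No new data and no change to design or analysis are needed.
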